6.6.2. Hypoglycemic Episode

According to the International Consensus Statement (Battelino et al. 2023), the CGM-determined hypoglycemic episodes for Level 1 or 2 and Level 2 are defined as below:

Hypoglycemia Level	Stating Time	Ending Time	Duration
Level 1 or 2 hypoglycemia	Time of the 1st BG of	Time of the last BG of the	Time of the last
(BG <70 mg/dL	BGs <70 mg/dL for	BGs \geq 70 mg/dL for	BG <70 mg/dL – time of
[3.9 mmol/L])	≥15 consecutive minutes	\geq 15 consecutive minutes	the 1st BG <70 mg/dL
Level 2 hypoglycemia (BG <54 mg/dL [3.0 mmol/L])	Time of the 1st BG of BGs <54 mg/dL for ≥15 consecutive minutes	Time of the last BG of the BGs \geq 54 mg/dL for \geq 15 consecutive minutes	Time of the last BG <54 mg/dL – time of the 1st BG <54 mg/dL
Level 2 hypoglycemia	Time of the 1st BG of	Time of the last BG that	Time of the last
ending with	BGs <54 mg/dL for	ensures the BGs ≥70 mg/dL	BG <70 mg/dL – time of
BG ≥70 mg/dL	≥15 consecutive minutes	for 15 consecutive minutes	the 1st BG <54 mg/dL

Abbreviation: BG = blood glucose (as captured in continuous glucose monitor [CGM]).

Note: Starting time and ending time are regardless of number of BG readings.

If the truncated time interval is >7 and \leq 15 minutes, linear interpolation will be used to impute the missing data at 5-minute intervals as described in Section 6.6.

If the truncated time interval is >15 minutes:

- at any time, which make the starting time undeterminable, then do not count this time interval and no episodes start.
- If it is after an episode started, which makes the ending time undeterminable, then the episode ends at the starting time of the truncation.
- If an episode started and continued until the end of a CGM session, then the episode ends at the end of CGM session.

The average duration, incidence, event rate of the Level 1 or 2 and Level 2 hypoglycemia episodes will be analyzed for each CGM session as planned in Section 4.6.3.1.2. The average duration will be calculated by dividing the sum of the duration of individual episodes during the given CGM session by the number of episodes and used in the analysis. The hypoglycemia event rate (events/participant/year) will be calculated by dividing the number episodes by the number of valid CGM days \times 365.25 days.

6.6.3. Mean Glucose and Glucose Management Indicator

The average glucose within a time period (a 24-hour period, daytime or nighttime) for each valid CGM day will be calculated first and then the average of daily average for a CGM session will be used as the mean glucose of the CGM session in the analysis.

The glucose management indicator (GMI) is a new parameter estimating A1c from CGM. The GMI is based on the above mean glucose (24-hour period) by CGM using the below formula (Bergenstal et al. 2018):

 $GMI(\%) = 3.31 + 0.02392 \times \text{mean glucose (mg/dL)}$

6.6.4. Glycemic Variability

Glycemic variability will be derived using the notation below:

i represents a time point within a time period (a 24-hour period, daytime or nighttime)

n represents the number of time points within the time period

k represents a valid CGM day within a visit

m represents the number of valid CGM days in the specific time period at a visit

 $BG_{k,i}$ represents the glucose value at time point *i* on day *k* unless otherwise specified.

Sections 6.6.4.1 and 6.6.4.2 provide the derivation method for variables assessing within-day and between-day glucose variability based on CGM readings.

6.6.4.2. Between-Day Variability

For variables assessing between-day variability, first determine the variability for each time point across days within a CGM session then average across all time points.

Between-day glucose SD (Rodbard 2009):

$$SD = \frac{1}{n} \sum_{i=1}^{n} SD_{i} = \frac{1}{n} \sum_{i=1}^{n} \sqrt{\frac{\sum_{k=1}^{m} (BG_{k,i} - \left\{\frac{\sum_{k=1}^{m} BG_{k,i}}{m}\right\})^{2}}{m-1}}$$

Between-day glucose CV (Kovatchev et al. 2009):

$$CV = \frac{1}{n} \sum_{i=1}^{n} CV_i = \frac{1}{n} \sum_{i=1}^{n} \frac{SD_i}{\left(\frac{\sum_{k=1}^{m} BG_{k,i}}{m}\right)} \times 100$$

Mean of daily differences (MODD): this parameter is calculated as the mean of absolute differences between glucose values at corresponding time points of consecutive days.

MODD =
$$\frac{1}{m-1} \sum_{k=1}^{m-1} \frac{\sum_{i=1}^{n} |BG_{k+1,i} - BG_{k,i}|}{n}$$

6.7. Appendix 7: MedDRA PT for Diabetic Retinopathy or Maculopathy

The following PT will be used to identify TEAEs of diabetic retinopathy or maculopathy (see Section 4.6.2.1.7):

- Amaurosis
- Amaurosis fugax
- Arteriosclerotic retinopathy
- Blindness
- Blindness transient
- Blindness unilateral
- Choroidal neovascularisation
- Cystoid macular oedema
- Detachment of macular retinal pigment epithelium
- Detachment of retinal pigment epithelium
- Diabetic blindness
- Diabetic eye disease
- Diabetic retinal oedema
- Diabetic retinopathy
- Diabetic uveitis
- Diplopia
- Exudative retinopathy
- Eye laser surgery
- Fundoscopy
- Fundoscopy abnormal
- Intra-ocular injection
- Macular detachment

- Macular oedema
- Maculopathy
- Noninfective chorioretinitis
- Noninfective retinitis
- Phacotrabeculectomy
- Retinal aneurysm
- Retinal arteriovenous malformation
- Retinal artery embolism
- Retinal artery occlusion
- Retinal artery stenosis
- Retinal collateral vessels
- Retinal cryoablation
- Retinal detachment
- Retinal exudates
- Retinal haemorrhage
- Retinal laser coagulation
- Retinal neovascularisation
- Retinal oedema
- Retinal operation
- Retinal thickening
- Retinal vascular disorder
- Retinal vascular occlusion
- Retinal vein occlusion
- Retinitis
- Retinopathy
- Retinopathy haemorrhagic
- Retinopathy hypertensive
- Retinopathy hyperviscosity
- Retinopathy proliferative
- Scintillating scotoma
- Sudden visual loss
- Venous stasis retinopathy
- Vision blurred
- Visual acuity reduced
- Visual acuity reduced transiently
- Visual impairment
- Vitrectomy

6.8. Appendix 8: MedDRA PT for Peripheral Edema

The analysis of peripheral edema (Section 4.6.2.1.8) will be based on the TEAEs in the following terms:

- Acute pulmonary oedema
- Ascites
- Brain oedema
- Bronchial oedema
- Capillary leak syndrome
- Cerebral oedema management
- Compression garment application
- Cytotoxic oedema
- Effusion

- Fluid retention
- Gastrointestinal oedema
- Generalised oedema
- Gravitational oedema
- Hydraemia
- Hypervolaemia
- Hypoosmolar state
- Lipoedema
- Lymphoedema
- Negative pressure pulmonary oedema
- Non-cardiogenic pulmonary oedema
- Non-pitting oedema
- Oedema
- Oedema blister
- Oedema due to cardiac disease
- Oedema due to hepatic disease
- Oedema due to renal disease
- Oedema mucosal
- Oedema peripheral
- Pelvic fluid collection
- Pericardial effusion
- Perinephric collection
- Perinephric oedema
- Peripheral swelling
- Pleural effusion
- Pulmonary oedema
- Retroperitoneal effusion
- Retroperitoneal oedema
- Skin oedema
- Skin swelling
- Subdural effusion
- Swelling
- Visceral oedema

6.9. Appendix 9: Empirical Estimation of Relative Event Rate

Traditionally, Poisson distribution has been assumed to draw inference for the rate of rare events. When the event is rare and the sample size is large, it is known that the overall number of events is approximately from Poisson distribution. However, for some not very rare events such as severe hypoglycemic events in T2D patients, the total number of events may not be distributed from Poisson and may be over-dispersed. Assuming Poisson distribution may significantly underestimate the variance, and therefore may reduce the overage probability and inflate the Type-I error. An empirical method in estimating the variance of the relative event rate without assuming any distribution on the number of events will be provided in this appendix.

Let X_{ij} denote the count response variable for patient *j* in treatment group *i*. Let $Y_i = \sum_j X_{ij}$ be the total number of events for treatment group *i*, and T_i denote the exposure for treatment group

i. Let i = 0 for the control group and i = 1 for the experimental treatment group. The event rate for treatment group *i* can be calculated as

$$\hat{r}_i = \frac{Y_i}{T_i}$$

The empirical variance of $\boldsymbol{\hat{r}}_{I}$ is

$$\widehat{Var}(\hat{r}_i) = T_i^{-2}\widehat{Var}(Y_i) = T_i^{-2}n_iS_i^2,$$

where S_i^2 is the variance of X_{ij} for treatment group *i*. Using the delta-method, the variance of $log(\hat{r}_i)$ can be estimated as

$$\widehat{Var}(\log(\hat{r}_i)) = Y_i^{-2} n_i S_i^2$$

The relative rate of the experimental treatment versus the control treatment is estimated as

$$\hat{\lambda} = \frac{\hat{r}_1}{\hat{r}_0}$$

The variances of $\hat{\lambda}$ and $\log(\hat{\lambda})$ are

$$\widehat{Var}(\hat{\lambda}) = \hat{\lambda}^2 \widehat{Var}(\log(\hat{\lambda}))$$
$$\widehat{Var}(\log(\hat{\lambda})) = \widehat{Var}(\log(\hat{r}_0)) + \widehat{Var}(\log(\hat{r}_1)) = Y_0^{-2} n_0 S_0^2 + Y_1^{-2} n_1 S_1^2$$

Assuming $\log(\hat{\lambda})$ is asymptotically from a normal distribution, the $100(1 - \alpha)\%$ confidence interval for $\log(\hat{\lambda})$ can be constructed as

$$\left[\log(\hat{\lambda}) - z_{1-\frac{\alpha}{2}}\sqrt{Var(\log(\hat{\lambda}))}, \log(\hat{\lambda}) + z_{1-\frac{\alpha}{2}}\sqrt{Var(\log(\hat{\lambda}))}\right]$$

Then, the $100(1 - \alpha)\%$ confidence interval for $\hat{\lambda}$ is

$$\left[\hat{\lambda}\exp\left(-z_{1-\frac{\alpha}{2}}\sqrt{\widehat{Var}(\log(\hat{\lambda}))}\right), \quad \hat{\lambda}\exp\left(z_{1-\frac{\alpha}{2}}\sqrt{\widehat{Var}(\log(\hat{\lambda}))}\right)\right]$$
(1)

The p-value for testing the null hypothesis of H_0 : $\lambda = 1$ is calculated as

$$p = 2\Phi\left(\frac{\left|\log(\hat{\lambda})\right|}{\sqrt{\widehat{Var}(\log(\hat{\lambda}))}}\right)$$
(2)

6.10. Appendix 10: Definition for Persistent/Recurrent Hypoglycemia

A P-R hypoglycemia based on programming search in the e-diary database for hypoglycemic events that meet prespecified criteria - is defined as a set of hypoglycemic episodes that:

a) starts with the occurrence of a level 3, or level 2 hypoglycemic episode (<54mg/dL, [3.0 mmol/L]) and is followed by more episodes of hypoglycemia (<70mg/dL, [3.9 mmol/L]), within the day of the initial episode,

AND

 b) is followed by at least one episode of hypoglycemia (<70mg/dL, [3.9 mmol/L]) per day, in the next 2 days or longer, and that ends when no hypoglycemia episode occurs for at least 2 days.

An example of a set of hypoglycemic episodes meeting the prespecified criteria for a P-R hypoglycemia event is illustrated in the figure below.

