## **Insulin Degludec Dose Adjustment**

## 6.1.6. Management of Hypoglycemia

At Visit 2 (Week -2), participants who have not screen failed will be trained by authorized site personnel about signs and symptoms of hypoglycemia and how to treat hypoglycemia and how to document episodes in the e-diary.

This section provides guidance on management of episodes of hypoglycemic events. For effective implementation of measures described here, it is important that participants, and their caregivers, if applicable, be well-educated about the signs and symptoms of hypoglycemia (for example, intense hunger, sweating, tremor, restlessness, irritability, depression, headaches, disturbed sleep, or transient neurological disorders) and its treatment. Participants should be instructed how to treat all levels of hypoglycemia and that if they experience an event of severe hypoglycemia, they should notify the site as soon as possible after the event has been successfully treated (see Section 8.3.3).

The allowable non-insulin antihyperglycemic medications are not insulin secretagogues; therefore, clinically relevant increases in the risk of hypoglycemia due to these medications are not expected. To date, effects of LY3209590 on hypoglycemia are not different as compared to other basal insulins, so the management of hypoglycemia is similar for the study participants in both treatment groups.

Study participants will be instructed to use standard precautions prior to and during exercise.

Study participants will be instructed to check their BG, when they experience signs and symptoms suggestive of hypoglycemia, and to administer appropriate treatment for when BG

 $\leq$ 70 mg/dL (3.9 mmol/L). They will be instructed to recheck BG levels 15 minutes following treatment of hypoglycemia and repeat treatment and BG recheck after another 15 minutes until the BG level has returned to the target range of 80-120 mg/dL (4.4-6.6 mmol/L) (CDC 2021). Instructions will be provided for clinical management of participants who experience frequent or repeated hypoglycemia. As necessary, additional instruction/education may be provided to participants by investigative staff, including increased BG monitoring, treatment adjustments, or other approaches (for example, behavioral interventions and lifestyle modification) to mitigate hypoglycemia frequency or severity.

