4.6.3. Additional Safety Assessments

4.6.3.1. Hypoglycemic Events

4.6.3.1.1. Participant-Reported Hypoglycemic Events

The following types of hypoglycemia events will be derived in the analysis data sets: documented hypoglycemia as Level 1, Level 2, and Level 3 (severe hypoglycemia) according to definitions based on the American Diabetes Association criteria where:

- Level 1: glucose <70 mg/dL (3.9 mmol/L) and $\ge 54 \text{ mg/dL}$ (3.0 mmol/L);
- Level 2: glucose < 54 mg/dL (3.0 mmol/L);
- Level 3: severe hypoglycemia (confirmed by the investigator to be an event that required assistance for treatment).

A set of Level 1 and Level 2 hypoglycemia events will be identified based on blood glucose reading values reported in the participant e-diary. A Level 3 hypoglycemia event is only confirmed by investigator and may not have an associated blood glucose reading.

If a hypoglycemic event is within 60 minutes of another hypoglycemic event, it is considered as a continuation of the previous event. If there are multiple events within 60 minutes of each other then all such events will be combined into a single episode with

- earliest date time and
- minimum glucose value, if applicable
- maximum severity (Level 1, 2 or 3)
- combining all symptoms and outcomes of the multiple hypoglycemic events.

The combined event starts from the first record with Level 1, 2 or 3, and ends when there are no more events for at least 60 minutes.

Further, all episodes will be classified as nocturnal (occurs between midnight and 0600) or nonnocturnal (occurs between 0600 and midnight) hypoglycemia by the time of the originating event.

The Level 2 and Level 3 events are considered as clinically significant hypoglycemia. Therefore, the analysis on a composite of Level 2 and Level 3 (denoted as Level 2/3) hypoglycemia will also be conducted.

The evaluation of potential persistent/recurrent hypoglycemia events will be through assessment of the clinically significant events confirmed by investigators based on clinical judgment and through events identified by pre-specified criteria (see Section 4.6.2.1.2 and Appendix 9 [Section 6.9] for details) using information based on the participant-reported hypoglycemia.

The details of planed analyses are provided in the table below.

Endpoint	Analysis Period	Statistical Method ^a
Event rate of Level 1	Baseline, 0-6, 0-12, 0-26, 0-52,	Negative binomial regression with treatment,

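### If the 60-minute merge applies to the programmed persistent-recurrent hypoglycemia definition, a long first-day low that is rechecked often is one episode and fails criterion (a), while the same low checked less often passes

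*SAP*

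**What the plan says.** SAP Section 6.10 (Appendix 10) gives the programmed definition of persistent-recurrent hypoglycemia. The event "is defined as a set of hypoglycemic episodes that" meets two conditions joined by AND:

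- (a) It begins with a Level 2 or Level 3 episode, "followed by more episodes of hypoglycemia (<70mg/dL, [3.9 mmol/L]), within the day of the initial episode".
- (b) The set "is followed by at least one episode of hypoglycemia (<70mg/dL, [3.9 mmol/L]) per day, in the next 2 days or longer".

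SAP Section 4.6.3.1.1 says how e-diary lows become episodes: "If there are multiple events within 60 minutes of each other then all such events will be combined into a single episode with" the earliest time, the lowest glucose and the highest severity level. The combined event "ends when there are no more events for at least 60 minutes". The same section says the pre-specified criteria draw on participant-reported hypoglycemia.

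Protocol Section 6.1.6 tells participants to recheck 15 minutes after treating a low and to "repeat treatment and BG recheck after another 15 minutes until the BG level has returned to the target range".

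The SAP version history shows Appendix 10 entering in Version 2, per regulatory input, and the 60-minute rule entering in Version 3. It lists no matching edit to Appendix 10.

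**The concern.** Appendix 10 counts episodes, and Section 4.6.3.1.1 uses that word for the merged unit. Rechecks made at the instructed interval during an unresolved low can then never produce a second episode, so criterion (a) cannot be met from that low, however long it lasts. Checking the same low less often breaks the chain and makes it countable.

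Persistent-recurrent hypoglycemia is a named safety topic of interest (SAP Section 4.6.2.1.2). The arms are compared on it by Fisher's exact test (SAP Section 4.6.3.1.1). A count that can fall as monitoring gets closer is hard to interpret as a measure of persistence.

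**Working it through.** The documents give no expected count for this event, so there is no plan figure to reproduce. The check applies the written rules to constructed e-diary sequences. The glucose courses are assumptions.

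**Inputs**
- Merge window: 60 minutes, chained (SAP 4.6.3.1.1).
- Criterion (a): first episode below 54 mg/dL or severe, plus further episodes below 70 mg/dL that day (Appendix 10).
- Criterion (b): at least one episode on each of the next 2 days (Appendix 10). It is taken as met, with one low on each day.
- Instructed recheck interval: 15 minutes (Protocol 6.1.6).

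**Formula.** A low lasting D minutes and read every s minutes gives n = floor(D/s) + 1 readings. If s is below 60 they chain into 1 episode. If s is above 60 they stay as n episodes.

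**Six-hour low, D = 360**

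| Spacing s (min) | Readings n | First-day episodes | (a) met? |
|---|---|---|---|
| 15 | 24 + 1 = 25 | 1 | No |
| 30 | 12 + 1 = 13 | 1 | No |
| 45 | 8 + 1 = 9 | 1 | No |
| 60 | 6 + 1 = 7 | 1 or 7 | Ambiguous |
| 75 | 4 + 1 = 5 | 5 | Yes |
| 90 | 4 + 1 = 5 | 5 | Yes |
| 120 | 3 + 1 = 4 | 4 | Yes |

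The 60-minute row is open because Section 4.6.3.1.1 merges an event that falls within 60 minutes of another, yet ends the episode after at least 60 minutes without one. Readings exactly 60 minutes apart satisfy both. The other rows hold whether more episodes means one further episode or two.

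**Duration, s = 15.** Lows of 1, 2, 6 and 12 hours give 5, 9, 25 and 49 readings. Merged, each is 1 episode and the definition is not met. If Appendix 10 were applied to unmerged readings, all four would meet it.

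**Other patterns**
- Two brief first-day lows 65 minutes apart, with recovery between: 2 episodes. The definition is met if one further episode is enough.
- The SAP's sensitivity rule, which merges until glucose reaches 70 mg/dL or more: the 6-hour low is 1 episode at spacings of both 15 and 90 minutes, so it does not recover the case.
- A 6-hour low on one day only: not met under any rule, because (b) fails.

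**The case against.** The strongest reply is that the collision is inferred. Appendix 10 never says the 60-minute merge applies, it also speaks of searching the e-diary database for hypoglycemic events, and its example figure is not shown in the text reviewed. This stands as a limit. The merged reading is the plain one, because Section 4.6.3.1.1 defines the episode and ties the criteria to participant-reported data, but it is not explicit. The two readings give opposite answers for the same low, so the silence itself needs correcting.

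Second, other analyses look for such events. The investigator route (SAP 4.6.2.1.2) can identify one, but it opens only after an e-diary report suggesting a potentially severe event, such as glucagon use or inability to self-treat. The CGM duration analyses and the listing of Level 2 episodes over 360 minutes cover scheduled sessions only. On treatment these are five of 4 weeks, 5 × 4 = 20 of 78 weeks.

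Third, the topic lies outside the multiplicity-adjusted objectives, and the recheck instruction and merge rule are common to both arms. That is correct and limits what is at stake.

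A reader might also infer more than the documents support:
- **That the plan misses persistent lows altogether.** It does not. Any further low outside the chain on the first day can satisfy (a), and the investigator route remains.
- **That merging is why a long single-day low is not counted.** Such a low fails (b) whatever the merge rule.
- **That the rule favors one arm.** Nothing in the documents shows this.
- **That the 17-day half-life makes this the specific concern, or that few events are expected.** Neither is stated. Protocol 6.1.6 says effects on hypoglycemia to date do not differ from other basal insulins.
- **That lows crossing midnight are wrongly dropped.** This depends on reading the day as a calendar day, which Appendix 10 does not specify.

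**Conclusion.** The point holds in a limited form. If Appendix 10 counts the merged episodes, a first-day low rechecked every 15 to 45 minutes is one episode and fails (a) at any duration. The same 6-hour low checked every 75 to 120 minutes gives 4 or 5 episodes and meets (a). Spacing of exactly 60 minutes is unresolved by the text.

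The programmed result changes only when two further conditions hold: (b) is met, and no separate low falls outside the merged chain that day. How many participants meet both conditions cannot be estimated from the documents. The order of the SAP versions makes an unintended interaction plausible but does not prove it.

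**What to change.** 1. In Appendix 10, state that the main row uses the merged episodes of Section 4.6.3.1.1, and keep the current definition as that row.
2. Add one supplementary programmed row. In it, (a) is also met when the initial merged Level 2 or 3 episode has lows spanning more than 60 minutes from first to last reading. The 60 minutes is the SAP's own merge window. Leave (b) unchanged on the following days, and let no low count toward both (a) and (b).
3. Report both counts by arm.
4. In Section 4.6.3.1.1, correct the cross-reference for the persistent-recurrent criteria from Appendix 9, which covers relative event rates, to Appendix 10.

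In the duration example, the 2-, 6- and 12-hour lows (spans of 120, 360 and 720 minutes) would enter the supplementary row. The 1-hour low (4 × 15 = 60 minutes, not more than 60) would not. A 6-hour low read at exactly 60-minute spacing would qualify whichever way it is merged.

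The first day should not be redefined as 24 hours. With a Level 2 low at 09:00, one low at 08:00 the next morning and one the day after, the 08:00 low could serve both (a) and (b). Three isolated daily lows would then count.

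The cost is a few lines of SAP text and programming on e-diary data already held. The downside is one extra row that departs from the definition received as regulatory input, which is why that definition stays as the main row. No treatment or recheck instruction changes.

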6.11. Appendix 11: Statistical Analysis for Japan

Separate analyses will be performed for participants participating in Study BDCU from Japan based on following subpopulations:

- Japanese population
- Japanese population whose prestudy basal insulin dose <10 U/day enrolled based on the I8H-MC-BDCU protocol addendum (2.1)
- Japanese population whose prestudy basal insulin dose $\geq 10 \text{ U/day}$

The analysis methods will be similar to those described for the main part of this statistical analysis plan. If there is not sufficient number of participants in the subpopulation, summary statistics will be provided instead. Efficacy analyses for Japan will be based on efficacy estimand for efficacy analyses.

The analyses to be included will be documented in a separate list of analyses which should include dispositions, demographics, and selected efficacy and safety endpoints.

Parameter (in conventional unit)	High/Low	Level 1	Level 2	Level 3		
General Chemistry						
Sodium (mFa/I)	Low	<132	<130	<125		
Source (mEq/L)	High	>150	>155	>160		
Potassium (mFa/I)	Low	<3.6	Level 2 I 2 <130 $ 0 >155 6 <3.4 5 >6 5 <88$	<3.0		
Totassium (mEq/L)	High	>5.5	>6	>6.5		
Chlorida (mEa/L)	Low	<95	<88	<80		
Chioride (mEq/L)	$\begin{array}{c c c c c c } \mbox{in (mEq/L)} & \begin{tabular}{ c c c } \hline High & >150 & >155 & >16 \\ \hline High & >150 & >155 & >16 \\ \hline High & >150 & >155 & >16 \\ \hline Low & <3.6 & <3.4 & <3. \\ \hline High & >5.5 & >6 & >6 & >6 \\ \hline Low & <95 & <88 & <88 & <88 \\ \hline High & >108 & >112 & >11 \\ \hline bonate (mEq/L) & $Low & <20 & <18 & <11 \\ \hline Low & <20 & <18 & <11 \\ \hline High & >108 & >12 & >11 \\ \hline Low & <20 & <18 & <11 \\ \hline High & >23 & >27 & >3 \\ \hline um (mg/dL) & $High & >10.5 & >11.0 & >12 \\ \hline phate (mg/dL) & $Low & <8.4 & <8.0 & <7. \\ \hline High & >10.5 & >11.0 & >12 \\ \hline phate (mg/dL) & $Low & <2.5 & <2.0 & <1. \\ \hline in (total) (g/dL) & $Low & <3.1 & <2.5 & <2. \\ Acid (urate) (mg/dL) & $High & >7.0 & $NA & $NA \\ \hline exp Function & & & \\ \hline timine (mg/dL) & $Increase & $\ge1.5 \times baseline & $\ge20\%$ decrease \\ from baseline & $from baseline & $from baseline \\ \hline seterol (total) (mg/dL) & $High & >200 & >240 & >30 \\ (mg/dL) in males & $Low & <40 & <30 & <22 \\ (mg/dL) in females & $Low & <40 & <30 & <22 \\ (mg/dL) in females & $Low & <50 & <40 & <20 \\ (mg/dL) & $High & >130 & >160 & >19 \\ \ ycerides (mg/dL) & $High & >150 & >300 & >50 \\ \hline atology & & \\ \hline the Blood Count & & \\ \hline C (cells/\muL) & $Low & <3500 & <3000 & <10. \\ \hline High & >10,800 & >13,000 & >15.0 \\ \hline \end{array}$	>115				
Disarkanata (mEa/L)	Low	<20	<18	<15		
Bicarbonate (mEq/L)	High	NA	NA	>30		
Blood urea nitrogen (mg/dL)	High	>23	>27	>31		
	Low	<8.4	<8.0	<7.5		
Calcium (mg/dL)	High	>10.5	>11.0	>12.0		
Phosphate (mg/dL)	Low	<2.5	<2.0	<1.4		
Protein (total) (g/dL)	Low	<6.0	<5.4	<5.0		
Albumin (g/dL)	Low	<3.1	<2.5	<2.0		
Uric Acid (urate) (mg/dL)	High	>7.0	NA	NA		
Kidney Function	8	,				
Creatinine (mg/dL)	Increase	$>1.5 \times$ baseline	$>2.0 \times \text{baseline}$	$>3.0 \times$ baseline		
		$\geq 25\%$ decrease	\geq 50% decrease	>75% decrease		
eGFR (ml/min/1.73m2)	Decrease	from baseline	from baseline	from baseline		
Linids			from ousenine	ironi ousenne		
Cholesterol (total) (mg/dL)	High	>200	>240	>300		
HDL (mg/dL) in males	Low	<40	<30	<20		
HDL (mg/dL) in females	Low	<50	<40	<20		
I DL (mg/dL)	$\frac{120}{110} \text{ In terms } \frac{120}{110} \text{ High} $		>160	>190		
Triglycerides (mg/dL) High >150		>150	>300	>500		
Hamatology						
Complete Blood Count						
Complete Blood Count	Low	<3500	<3000	<1000		
WBC (cells/µL)	High	>10 800	>13 000	>15 000		
	Ingn	> 10,000	>15,000	>15,000		
	Decrease	NA	from baseline	>2 decrease nom		
Hemoglobin (g/dL)			>2 increase from	>3 increase from		
	Increase	NA	>2 increase nom	> 5 mercase nom		
Distalats (calls/uL)	Low	<140.000	<125 000			
Hemoglobin male (g/dL)	Low	12 5 13 5	<125,000	<10,000		
Hemoglobin, finale (g/dL)	Low	11.0 12.0	<12.5	<10.5		
WPC Differential	$\begin{array}{c ccccccccccccccccccccccccccccccccccc$					
WBC Differential	Law	<1000	<750	<500		
Lymphocytes (cells/µL)	LOW	<1000	>10000	>20000		
	High	>4000	>10000	>20000		
$\frac{1}{1} = \frac{1}{1} \left(\frac{1}{1} + \frac{1}{1} \right)$	LOW	<2000	<1000 >1500	<pre><300</pre>		
Eosmophils (cens/µL) Hign >000 >1000 >5000				>5000		
Coagulation Studies	т	. 1 1 . TTT .		5 1 7 TT 5 T		
Prothrombin Time (seconds)	Increase	>1.1 × ULN	$>1.3 \times ULN$	>1.3 × ULN		

